6.2.1.2. Secondary Endpoints

- Percent of subjects with ≥ 4 point reduction from baseline in SELENA SLEDAI score assessed every 24 weeks.
- Number of days of daily prednisone dose ≤ 7.5 mg/day and/or reduced by 25% from baseline over time.
- Time to first severe SLE Flare Index (SFI) flares assessed over time.

NOTE: Baseline will be defined as study Day 0 of BEL113750 study or C1115 study as appropriate. Additionally, for the group of subjects who received placebo in BEL113750, a secondary analysis will be performed by defining the baseline as Day 0 of the current study the day placebo subjects in BEL113750 will have begun to receive belimumab treatment. (See Section 8.1)

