Section 8.1.1. Primary Efficacy Analysis and Section 8.1.2 Analysis of Additional Efficacy and Biomarkers Subjects who received subcutaneous (SC) belimumab in the BEL112341 study before joining the BEL114333 study will be evaluated separately.	Although the efficacy data for BEL112341 subjects in this section were to be analysed separately, the data will be combined with the data from subjects who received IV belimumab in the BEL113750 parent study.	There are no clinically significant differences in the results between these studies in terms of which formulation was used. Hence, the data from these 25 SC subjects can be aggregated with the subjects who received the IV formulation, unless otherwise stated.
Section 6.2.1.2 Secondary [Efficacy] Endpoints Baseline will be defined as study Day 0 of the respective studies BEL113750 or BEL112341.	For subjects randomised to placebo during the parent study BEL113750, baseline will be defined as study Day 0 of the study BEL114333. For subject randomised to placebo in the parent study BEL112341, baseline will be defined as study Day 0 of the open-label extension of BEL112341.	For consistency with the LTC studies, baseline is defined as the last available value prior to the initiation of treatment with belimumab. No additional analyses are planned as mentioned in the protocol, for placebo.
Section 6.2.1.1 Primary Endpoint The SRI response is defined as the primary efficacy endpoint.	The primary SRI response endpoint will be regarded as a key secondary endpoint for the study BEL114333.	The primary objective of the study BEL114333 is safety. Efficacy is considered as a secondary outcome.
Section 6.2.1.2 Secondary [Efficacy] Endpoints	PGA and BILAG components of the SRI response endpoint were added.	Additional analyses are being reported to enable the long-term data to be further evaluated.
Section 6.2.1.2 Secondary [Efficacy] Endpoints Number of days of daily prednisone dose ≤ 7.5 mg/day and/or reduced by 25% from baseline over time.	The threshold of a 25% reduction has been revised to 50%.	For consistency with the BEL113750 parent study definition of this endpoint. This endpoint was not considered in the parent study BEL112341.

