8.1.4. BILAG No New 1A/2B Organ Domain Scores

The proportion of subjects with no new BILAG A and at most 1 new BILAG B organ domain scores (No New 1A/2B) compared to baseline at the time of the assessment, will be summarised by parent randomised treatment group, and the total Safety population, for each belimumab visit (every Week 24 and Week 48 visit). Total Safety population data will be displayed graphically using a line graph.

8.1.5. Number of Days of Daily Prednisone ≤ 7.5 mg/day and/or Reduced by 50% from Baseline

The number of days of daily prednisone dose ≤ 7.5 mg/day and/or reduced by 50% from baseline will be summarised at each Week 24 and 48 belimumab visit (in every year) and at any time post-baseline. Only subjects receiving a prednisone dose ≥ 7.5 mg/day at the baseline visit will be included.

For subjects who have attended Week 24 and 48 belimumab visits (in every year), the number of days from first day of belimumab (given on the baseline visit) of daily prednisone dose ≤ 7.5 mg/day and/or reduced by 50% compared to the baseline visit will be summarised, using descriptive statistics.

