8.2.11. Prednisone Percent Change from Baseline

The observed values and percent change from baseline in average daily prednisone dose will be summarised using descriptive statistics, and presented by the parent randomised treatment group and the total Safety population, for each Week 24 and 48 belimumab visit (in every year).

The derivation of average daily prednisone dose and conversion to the prednisone-equivalent dose are provided in Section 11.5.3

Total Safety population data will be displayed graphically using a line graph. The plot will show the mean percent change from baseline (\pm SE) over time.

8.2.12. Prednisone Dose ≤ 7.5 mg/day for Subjects with an Average Daily Dose > 7.5 mg/day at Baseline

For subjects with an average daily prednisone dose > 7.5 mg/day at baseline, the proportion of subjects with an average daily prednisone dose reduced to ≤ 7.5 mg/day will be summarised, and presented by the parent randomised treatment group, and overall, for each Week 24 and Week 48 belimumab visit (in every year).

For this group of subjects having an average daily prednisone dose > 7.5 mg/day at baseline, the data showing reduction to ≤ 7.5 mg/day will be displayed graphically using a line graph. The plot will show the proportion of subjects with this reduction (\pm SE) over time.

8.2.13. Prednisone Dose > 7.5 mg/day for Subjects with an Average Daily Dose ≤ 7.5 mg/day at Baseline

For subjects with an average daily dose ≤ 7.5 mg/day at baseline, the proportion of subjects with an average daily prednisone dose increased to > 7.5 mg/day, will be summarised, and presented by the parent randomised treatment group, and the overall, for each Week 24 and Week 48 belimumab visit (in every year).

For this group of subjects having an average daily prednisone dose \leq 7.5 mg/day at baseline, the data showing elevation to > 7.5 mg/day will be displayed graphically using a line graph. The plot will show the proportion of subjects with this increase (\pm SE) over time.

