11.2.2. Belimumab Visits

- For summaries performed by belimumab visit, placebo subjects are aligned based on start of exposure to belimumab.
- Baseline for both belimumab and placebo randomized subjects will be the last non-missing value prior to or on the first treatment date, except for corticosteroid use, which is the last 7 days prior to treatment start date.
- Visits will be aligned so that each visit represents equivalent exposure time to belimumab, regardless of parent study treatment, and will be mapped accordingly based on the endpoint and scheduled visits collected.

	BEL1	13750	BEL1	12341
Belimumab	Parent Randomize	d Study Treatment	Parent Randomize	d Study Treatment
Visit Name	Belimumab	Placebo	Belimumab	Placebo
		PS Week 52/		
Year 1 Day 0	PS Week 0	OL Year 1 Week 0	Day 0	Day 364/Exit
Year 1 Week 4	PS Week 4	OL Year 1 Week 4	PS Day 28	PS Day 28 OLE
Year 1 Week 8	PS Week 8	OL Year 1 Week 8	PS Day 56	
Year 1 Week 12	PS Week 12	OL Year 1 Week 12	PS Day 84	PS Day 84 OLE
Year 1 Week 16	PS Week 16	OL Year 1 Week 16	PS Day 112	
Year 1 Week 20	PS Week 20	OL Year 1 Week 20	PS Day 140	
				PS Day 168 OLE/
Year 1 Week 24	PS Week 24	OL Year 1 Week 24	PS Day 168	OL Year 1 Week 0
Year 1 Week 28	PS Week 28	OL Year 1 Week 28	PS Day 196	OL Year 1 Week 4
Year 1 Week 32	PS Week 32	OL Year 1 Week 32	PS Day 224	OL Year 1 Week 8
Year 1 Week 36	PS Week 36	OL Year 1 Week 36	PS Day 252	OL Year 1 Week 12
Year 1 Week 40	PS Week 40	OL Year 1 Week 40	PS Day 280	OL Year 1 Week 16
Year 1 Week 44	PS Week 44	OL Year 1 Week 44	PS Day 308	OL Year 1 Week 20
	PS Week 52/OL			
Year 1 Week 48	Year 1 Week 0	OL Year 1 Week 48	PS Day 364/Exit	OL Year 1 Week 24
	is not mapped to a belim			other visits and
	t is used for any derivation			OL Vanid Wask 20
Year 2 Week 4	OL Year 1 Week 4	OL Year 2 Week 4	PS Day 28 OLE	OL Year 1 Week 28
Year 2 Week 8	OL Year 1 Week 8	OL Year 2 Week 8	DO D 04 01 E	OL Year 1 Week 32
Year 2 Week 12	OL Year 1 Week 12	OL Year 2 Week 12	PS Day 84 OLE	OL Year 1 Week 36
Year 2 Week 16	OL Year 1 Week 16	OL Year 2 Week 16		OL Year 1 Week 40
Year 2 Week 20	OL Year 1 Week 20	OL Year 2 Week 20		OL Year 1 Week 44
V 0W 104	01.77	01.1/ 01/1/ 1.04	PS Day 168 OLE/	01.7/ 4.7/ 1.40
Year 2 Week 24	OL Year 1 Week 24	OL Year 2 Week 24	OL Year 1 Week 0	OL Year 1 Week 48
Year 2 Week 28	OL Year 1 Week 28	OL Year 2 Week 28	OL Year 1 Week 4	OL Year 2 Week 4
Year 2 Week 32	OL Year 1 Week 32	OL Year 2 Week 32	OL Year 1 Week 8	OL Year 2 Week 8

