- Concomitant medications, including corticosteroids, were collected in both the parent studies and BEL114333. To determine average daily dose and for analysis of steroid use, all steroid dosages are converted to a prednisone equivalent dosage in milligrams.
- The average daily prednisone dose considers all steroids taken systemically intravenously (IV), intramuscularly (IM), SC, intradermally, and orally for both SLE and non-SLE reasons.
- At baseline, the average daily prednisone dose is the sum of all prednisone doses over 7 consecutive days up to, but not including Day 0, divided by 7.
- While on treatment, the average daily prednisone dose is the sum of all prednisone doses over 7 consecutive days, including the day of interest, divided by 7, unless otherwise specified.
- This average dose will be categorised as 0, >0 to ≤7.5, >7.5 to ≤40, and >40 mg/day. The
 average daily prednisone dose will be calculated for weeks 24 and 48 for each year.

Prednisone Equivalent Daily Dose Conversions

- At data base lock, all preferred terms identified with an ATC code beginning with 'H02' will be
 reviewed to ensure a conversion factor exists for all terms with a systemic or intra-articular route
 of administration.
- Similarly, all routes of administration for preferred terms
- Reported dose of systemic steroid is converted to prednisone equivalent dose using a conversion factor for each medication (refer to online calculator http://www.globalrph.com/corticocalc.htm).
 - Prednisone equivalent dose (mg/day) =
 Collected dose (mg) x Conversion Factor x Frequency Factor

[figure not shown]
Preferred Term	Conversion Factor for Prednisone-Equivalent Dose (mg)					
BETAMETHASONE	8.333					
BETAMETHASONE DIPROPIONATE	8.333					
BETAMETHASONE SODIUM PHOSPHATE	8.333					
BUDESONIDE	No conversion applied – nasal spray taken by 1 subject in BEL113750					
CELESTONA BIFAS	7.5					
CORTISONE	0.2					
CORTISONE ACETATE	0.2					
DEFLAZACORT	5/6					
DEPO-MEDROL MED LIDOKAIN	1.25					
DEXAMETHASONE	6.667					
DEXAMETHASONE ACETATE	6.667					
DEXAMETHASONE SODIUM PHOSPHATE	6.667					
FLUOCORTOLONE	3					
HYDROCORTISONE	0.25					
HYDROCORTISONE ACETATE	0.25					
HYDROCORTISONE SODIUM SUCCINATE	0.25					
MEPREDNISONE	1.25					

[figure not shown]
METHYLPREDNISOLONE	1.25
METHYLPREDNISOLONE ACETATE	1.25
METHYLPREDNISOLONE SODIUM SUCCINATE	1.25
PARAMETHASONE	2.5
PREDNISOLONE	1
PREDNISOLONE ACETATE	No conversion applied - conjunctival
PREDNISOLONE SODIUM PHOSPHATE	1

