11.12.6. Efficacy Tables

Efficacy	y : Tables				
No.	Population	Example Shell	Title	Programming Notes	Final Deliverable [Stage]
SRI and	Secondary Ef	ficacy Endpoints			•
3.1.	Safety	EFF_T1	SRI Response by Belimumab Visit		
3.2.	Safety	EFF_T1	SELENA SLEDAI (≥ 4 Point Reduction from Baseline) by Belimumab Visit		
3.3.	Safety	EFF_T1	PGA No Worsening (Increase of < 0.30 points from Baseline) by Belimumab Visit		
3.4.	Safety	EFF_T1	BILAG No New 1A/2B Organ Domain Scores Compared to Baseline by Belimumab Visit		
3.5.	Safety	EFF_T2	Number of Days of Daily Prednisone ≤ 7.5 mg/day and/or Reduced by 50% from Baseline, Among Subjects with Baseline Daily Prednisone Dose > 7.5 mg/day		
3.6.	Safety	EFF_T3	Time to First Severe SFI Flare		
3.7.	Safety	EFF_T4	Number of Subjects with At Least One Severe SFI Flare by Belimumab Visit		
Other E	fficacy Endpoi	nts: Disease Acti	vity		
3.8.	Safety	EFF_T5	SELENA SLEDAI (Observed and Change from Baseline) by Belimumab Visit		
3.9.	Safety	EFF_T5	SELENA SLEDAI (Observed and Percent Change from Baseline) by Belimumab Visit		
3.10.	Safety	EFF_T5	SLICC/ACR Damage Index (Observed and Change from Baseline) by Belimumab Visit (Subjects from Parent Study BEL113750)		

Efficac	Efficacy: Tables								
No.	Population	Example Shell	Title	Programming Notes	Final Deliverable [Stage]				
3.11.	Safety	EFF_T5	SLICC/ACR Damage Index (Observed and Change from Baseline) by Belimumab Visit (Subjects from Parent Study BEL112341)						
3.12.	Safety	EFF_T1	SLICC/ACR Damage Worsening (Change > 0) from Baseline by Belimumab Visit (Subjects from Parent Study BEL113750)						
3.13.	Safety	EFF_T1	SLICC/ACR Damage Worsening (Change > 0) from Baseline by Belimumab Visit (Subjects from Parent Study BEL112341)						
3.14.	Safety	EFF_T5	PGA (Observed and Percent Change from Baseline) by Belimumab Visit						
Other E	fficacy Endpoi	nts: Flares			·				
3.15.	Safety	EFF_T3	Time to First SFI Flare						
3.16.	Safety	EFF_T4	Number of Subjects with At Least One SFI Flare by Belimumab Visit						
3.17.	Safety	EFF_T6	Total Number of Severe SFI Flares (Rate per 100 Person-Years)						
3.18.	Safety	EFF_T6	Total Number of SFI Flares (Rate per 100 Person-Years)						
3.19.	Safety	EFF_T3	Time to First 1A/2B BILAG Flare						
3.20.	Safety	EFF_T4	Number of Subjects with At Least One 1A/2B BILAG Flare by Belimumab Visit						
3.21.	Safety	EFF_T3	Time to First BILAG A Flare						
3.22.	Safety	EFF_T4	Number of Subjects with At Least One BILAG A Flare by Belimumab Visit						

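### SAP 8.1.5 admits a baseline prednisone dose of exactly 7.5 mg/day, which its own Table 3.5 excludes; an unchanged 7.5 mg/day then counts as a qualifying day every day

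*SAP*

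**What the plan says.** **The endpoint.** Protocol 6.2.1.2 lists it as "Number of days of daily prednisone dose ≤ 7.5 mg/day and/or reduced by 25% from baseline over time", with no restriction on baseline dose. SAP Section 2.1, Table 1, records one change: "The threshold of a 25% reduction has been revised to 50" percent, made to match the definition in parent study BEL113750.

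**The SAP text.** Section 8.1.5 adds a baseline restriction: "Only subjects receiving a prednisone dose ≥ 7.5 mg/day at the baseline visit will be included". It summarises the day count at each Week 24 and Week 48 visit and at any time post-baseline.

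**The SAP output.** Table 12 plans a table and a listing for this endpoint but no figure. Appendix 12 lists one table, Table 3.5, whose title ends "Among Subjects with Baseline Daily Prednisone Dose > 7.5 mg/day".

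**Neighbouring rules.** Section 8.2.12 applies "For subjects with an average daily prednisone dose > 7.5 mg/day at baseline". Its complement, Section 8.2.13, is headed "for Subjects with an Average Daily Dose ≤ 7.5 mg/day at Baseline". The dose bands in Sections 6.2.1.1, 7.1.3, 7.1.4 and 11.5.3 all put exactly 7.5 in the lower band.

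**Baseline steroid dose.** Section 11.5.3 says "At baseline, the average daily prednisone dose is the sum of all prednisone doses over 7 consecutive days", ending before Day 0 and divided by 7. Section 11.2.2 uses the last non-missing value for baseline "except for corticosteroid use, which is the last 7 days prior to treatment start date". Section 8.1.5 refers only to the baseline visit.

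**The concern.** The text and the table title define two populations for one listed secondary endpoint, so the result depends on which line the programmer follows. The difference matters because 7.5 mg/day is both the entry threshold and the target. With ≥ at entry and ≤ at the target, a subject at exactly 7.5 enters already meeting the target, and no change in dose is counted as steroid sparing. The same subject would also sit in the low-dose population of Section 8.2.13. Table 3.5 could then contain subjects whom Table 3.28, with an equivalent >7.5 title, leaves out.

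A second, smaller issue concerns the any-time row. A raw count of days grows with length of follow-up, and follow-up differs by design between the two display groups and within each of them. The SAP text asks for no denominator.

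**Working it through.** The documents give no figure for this endpoint to reproduce, so the check applies the stated rules directly.

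**1. Boundary.** A day qualifies if dose ≤7.5 or dose ≤0.5 × baseline. For a subject whose dose never changes:

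| Baseline dose (mg/day) | In under ≥7.5 | In under >7.5 | Qualifying days of 168 | Qualifying days of 336 |
|---|---|---|---|---|
| 7.4 | no | no | 168 | 336 |
| 7.5 | yes | no | 168 | 336 |
| 7.6 | yes | yes | 0 | 0 |
| 10 | yes | yes | 0 | 0 |

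Under >7.5, every included subject with an unchanged dose scores 0. Under ≥7.5, the subject at exactly 7.5 scores the maximum.

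**2. Effect on the mean.** The share *p* of included subjects unchanged at exactly 7.5 is not in the documents, nor is the mean *m* of the others, so both are assumed. At Week 24 the mean rises by *p* × (168 − *m*).

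- With *m* = 84: *p* = 0, 0.05, 0.10 gives 0, 4.2, 8.4 days.
- With *m* = 0: the same shares give 0, 8.4, 16.8 days.

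**3. Unequal follow-up in the any-time row.** These are days from first belimumab dose to the last visit mapped in SAP 11.2.2, with a 48-week year of 336 days:

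- BEL113750 belimumab (OL Year 7 Week 4): 364 + 6×336 + 28 = 2408
- BEL113750 placebo (OL Year 7 Week 4): 6×336 + 28 = 2044
- BEL112341 belimumab (OL Year 4 Week 24): 364 + 168 + 3×336 + 168 = 1708
- BEL112341 placebo (OL Year 4 Week 32): 168 + 3×336 + 224 = 1400

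Between display groups the ratio is 2408/2044 = 1.18. If both groups qualified on 50% of days, the counts would be 1204 and 1022. SAP Table 1 pools the 25 BEL112341 subjects with the others, so the ratios within columns are 2408/1708 = 1.41 and 2044/1400 = 1.46. These are schedule maxima, not observed follow-up.

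Korean follow-up also stopped early. The last visit there was 27 April 2015 (SAP 3.2) and the last dose in the study was in March 2018 (SAP 5.1), a gap of 1039 days to 1 March or 1069 days to 31 March.

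**4. End of the counting window.** SAP 2.4.1 runs analyses to study end, and SAP 11.2.1 includes follow-up visits in the any-time period. Protocol Table 2 schedules concurrent medication up to the 16-week follow-up but not at 6 months. SAP 11.6.2.1 treats medication with a missing end date as ongoing. Taking 6 months as 182 days (assumed), 182 − 112 = 70 days could be counted after the last scheduled medication record.

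**The case against.** The strongest reply is that this is a one-symbol mismatch in a descriptive endpoint with no hypothesis test, affecting perhaps nobody, and that the Table 3.5 title already carries the strict rule. The size is indeed unknown, and the illustrated shift depends entirely on assumed shares. But the title does not settle the matter, because Section 8.1.5 is the analysis specification and says the opposite.

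A second reply is that the SAP aligns this endpoint with a parent-study definition that is not in the documents, and that Sections 8.2.12 and 8.2.13 concern average daily dose rather than days. Both statements are true, so the direction of the correction rests on internal consistency. That consistency is strong: Table 3.5, Section 8.2.12, Table 3.28, every dose band, and the related endpoint in Protocol 6.2.1.3 (from above 7.5 to 7.5 or less) all place exactly 7.5 in the lower group. If the parent definition did use ≥, an unchanged 7.5 would still qualify every day.

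On the any-time row, several mitigations stand:

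- By-visit rows are limited to attenders.
- The SAP discloses the one-year offset between groups (5.1).
- Person-years are tabulated separately (Table 1.3).
- Other prednisone summaries do not accumulate days.
- The any-time rule in Section 11.2.1 sits in an appendix introduced as windowing for safety endpoints, so its application here is not certain.
- Medications starting after the 16-week visit have their own listing (Listing 55).
- Last visit to last visit, the Korea–Japan gap is 1235 days (27 April 2015 to 13 September 2018), but Korea is not a display column.

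These points keep the any-time issue secondary. They do not give the row a denominator.

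**Conclusion.** The point holds. As written, the inclusion rule in Section 8.1.5 contradicts the endpoint's only table and credits a subject unchanged at exactly 7.5 mg/day with every counted day. It should be corrected. The effect is confined to subjects at exactly 7.5 mg/day at baseline: the maximum per subject is all counted days, and the aggregate effect is unknown and possibly zero. The restriction itself is an SAP addition that Table 1 does not record.

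The any-time issue is a worthwhile improvement rather than an error. The SAP already adjusts for follow-up in its AE rates (7.2.2) and SFI flare rates (8.2.5). Listings would let a reader rebuild each subject's share of days, but the text asks for no summary of it. The Table 3.5 shell is in a separate document, so whether it already shows days observed cannot be checked here.

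**What to change.** 1. In Section 8.1.5, change the analysis inclusion rule to baseline prednisone >7.5 mg/day and tie it to the 7-day baseline average in Sections 11.2.2 and 11.5.3. This matches Table 3.5 and Section 8.2.12.
2. In SAP Table 1, list the baseline restriction as a change from the protocol.
3. As a secondary improvement, keep the protocol's day count in the any-time row and add qualifying days as a percentage of days observed. Use one window for numerator and denominator, ending at the latest scheduled visit where concurrent medication was recorded, up to the 16-week follow-up. This parallels the last-contact rule for AE rates in Section 7.2.2.

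The cost is two small wording edits in 8.1.5, one sentence on the window, one line in Table 1 and one extra row in Table 3.5. If the ≥ rule was programmed, any subjects at exactly 7.5 mg/day leave the table. No new data are needed.

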8.1.6. Time to First Severe SFI Flare

SFI flare data are collected at scheduled visits where only one flare may be recorded. The frequency of these flare assessments vary and will be collected in accordance to their respective timings (Section 11.1). Additional flares occurring between scheduled assessments during study BEL114333 were collected using an additional SLE flare log. (Note: only the flare data were collected but no visit information) and flares will be assigned to the next scheduled visit for flares.

Time to the first severe SFI flare during belimumab treatment will be summarised by the parent randomised treatment group, and the total Safety population.

Note, for this study, analyses of SFI flares will be conducted based on the modified SLE flare index (modified excludes severe flares from the SELENA SLEDAI assessment that were triggered only by an increase in SELENA SLEDAI score to > 12, see Section 11.5.4.5).

Only post-baseline flares will be considered in these analyses. Flares (not subjects) occurring on the first belimumab dose date should be removed from the analysis dataset prior to determining the first flare.

Time to the first severe SFI flare is calculated as the number of days from the first dose of belimumab treatment up to the first severe flare event (event date – first dose date of belimumab + 1). The disposition of subjects is defined as follows:

Subject Disposition	Event Met	Event Date
Subject has a severe SFI flare		
Subject has a severe SFI flare during the study	Yes	Date of first severe SFI flare
Subject does not have a severe SFI flare		
Subject withdraws from the study	No	Censored at last available date where flare is assessed
Subject dies during the study	No	Censored at date of death.
Subject who completes the study *	No	Censored at last available date where flare is assessed

^{*} As per the protocol. Includes subjects who transferred to study BEL116027, or who were still participating in the study at the time of the sponsor decision to close the study.

The display will summarise the number and percentage of subjects with a severe SFI flare as well as the Kaplan-Meier estimate of the median, 25th and 75th percentiles of days to first severe SFI flare. For subjects who experienced a severe SFI flare, the display will summarise the median, 25th and 75th percentiles, minimum and maximum time to the first severe SFI flare from baseline, by parent randomised treatment group, and the total Safety population.

A cumulative incidence curve for time to first severe SFI flare will be produced for the total Safety population, using Kaplan-Meier methods. The time of the first severe SFI

flare from baseline through to each belimumab visit at Week 24 and Week 48 of each year will be summarised.

